1 SYNOPSIS

Protocol Title: An Open-label, Multi-center Extension Study to Evaluate the Long-term Safety and Efficacy of Deucravacitinib in Participants with Moderate to Severe Crohn’s Disease or Moderate to Severe Ulcerative Colitis

Short Title: Long-term Safety and Efficacy of Deucravacitinib in Participants with Crohn’s Disease or Ulcerative Colitis

Study Phase: 2

Rationale:

IM011077 is an open-label, long-term extension study designed to evaluate the long-term safety and efficacy of deucravacitinib (BMS-986165) 6 mg twice daily (BID) in participants who have previously been enrolled in a Phase 2 deucravacitinib study for moderate to severe Crohn’s disease (CD) (Study IM011023) or moderate to severe ulcerative colitis (UC) (Studies IM011024 and IM011127).

Study Population: Adults with CD or UC who have completed participation in a preceding study, including Studies IM011023, IM011024, or IM011127, may be eligible to enroll in Study IM011077.

Objectives and Endpoints - Crohn’s Disease

Objective	Endpoint
Primary	

To assess the safety and tolerability of long-term use of deucravacitinib in participants with moderate to severe CD.	
Number and proportion of participants experiencing AEs, SAEs, AEs leading to study discontinuation, and AEIs.Number and proportion of participants experiencing abnormalities in laboratory testing, ECG, and vital sign parameters over time.Changes from Day 1 for laboratory testing, ECG, and vital signs.

Exploratory	
A large black rectangular redaction box covering the entire content of the Exploratory section.	

Objective	Endpoint

Abbreviations: AE = adverse event; AEI = adverse event of interest; CD = Crohn’s disease; ECG = electrocardiogram;

SAE = serious adverse event;

Objectives and Endpoints - Ulcerative Colitis:

Objective	Endpoint
Primary	

 To assess the safety and tolerability of long-term use of deucravacitinib in participants with moderate to severe UC. 	
 Number and proportion of participants experiencing AEs, SAEs, AEs leading to study discontinuation, and AEIs. Number and proportion of participants experiencing abnormalities in laboratory testing, ECG, and vital sign parameters over time. Changes from baseline for laboratory testing, ECG, and vital signs.
Exploratory	

Objective	Endpoint
[REDACTED]	

[figure not shown]

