4 OBJECTIVES AND ENDPOINTS

Table 4-1: Objectives and Endpoints - Crohn’s Disease

Objective	Endpoint ^a
Primary	

 To assess the safety and tolerability of long-term use of deucravacitinib in participants with moderate to severe CD. 	
 Number and proportion of participants experiencing AEs, SAEs, AEs leading to study discontinuation, and AEs. Number and proportion of participants experiencing abnormalities in laboratory testing, ECG, and vital sign parameters over time. Changes from Day 1 for laboratory testing, ECG, and vital signs.
Exploratory	

[figure not shown]

Table 4-1: Objectives and Endpoints - Crohn’s Disease

Objective	Endpoint ^a
[Redacted Content]	

Abbreviations: AE = adverse event; AEI = adverse event of interest; CD = Crohn’s disease; ECG = electrocardiogram;

[Redacted Content] SAE = serious adverse event;

^a See [Section 10.4.1.1](#) for the definition of baseline for efficacy assessments.

Table 4-2: Objectives and Endpoints - Ulcerative Colitis

Objective	Endpoint ^a
[Redacted Content]	
Primary	

 To assess the safety and tolerability of long-term use of deucravacitinib in participants with moderate to severe UC. 	
 Number and proportion of participants experiencing AEs, SAEs, AEs leading to study discontinuation, and AEIs. Number and proportion of participants experiencing abnormalities in laboratory testing, ECG, and vital sign parameters over time. Changes from baseline for laboratory testing, ECG, and vital signs.
Exploratory	
[Redacted Content]	

Table 4-2: Objectives and Endpoints - Ulcerative Colitis

Objective	Endpoint ^a
[Redacted content]	

Abbreviations: AE = adverse event; AEI = adverse event of interest; ECG = electrocardiogram;

[Redacted content] SAE = serious adverse event; [Redacted content] UC = ulcerative colitis; [Redacted content]

^a See [Section 10.4.1.1](#) for the definition of baseline for efficacy assessments.

Table 4-3: Selected Endpoint Definitions

Endpoint	Definition
[Redacted content]	

Table 4-3: Selected Endpoint Definitions

Endpoint	Definition
[Redacted content]	

Table 4-3: Selected Endpoint Definitions

Endpoint	Definition
[Redacted]	
[Redacted]	[Redacted]
[Redacted]	[Redacted]
[Redacted]	[Redacted]
[Redacted]	[Redacted]
[Redacted]	[Redacted]
[Redacted]	[Redacted]

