7.7.4 Disease Exacerbation, Corticosteroid Rescue Therapy, and Tapering

7.7.4.1 Disease Exacerbation

Participants who are experiencing symptoms of possible disease exacerbation (loss of response for CD or disease worsening for UC as defined in [Table 4-1](#) and [Table 4-2](#)) should be evaluated as deemed appropriate by the investigator in order to determine whether corticosteroid rescue therapy may be appropriate. Participants who are seen by the investigator due to disease exacerbation should undergo the following assessments:

- Symptom-directed physical examination including vital signs
- Assessment of disease activity

- [REDACTED] complete blood count, and additional laboratory assessments, as indicated
- Stool sample for culture, ova, and parasite evaluation, and *Clostridioides. difficile* assay
- [REDACTED]
- Endoscopy may be considered and performed

Upon confirmation of loss of response or disease worsening, corticosteroid rescue therapy or alternative efficacious therapy for IBD may be initiated. If the participant still meets the criteria for loss of response or disease worsening [REDACTED] after first presenting with symptoms and despite treatment, he/she should be identified as a treatment failure, be discontinued from study treatment (Sections 5.1.4 and 8.1), and enter the post-treatment follow-up period (Section 5.1.3).

If an alternative, efficacious therapy for IBD is determined to be the appropriate course of action, the participant will be identified as a treatment failure and must be discontinued from study treatment (Sections 5.1.4 and 8.1).

Corticosteroid rescue therapy and the subsequent tapering is described in detail in Section 7.7.4.2.

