7.7.4.2 Corticosteroid Rescue Therapy and Tapering

[REDACTED]

[REDACTED] Failure to taper the corticosteroid dose to 0 mg daily [REDACTED] of initiation will be considered treatment failure, and participants must discontinue from the study, unless the participants require glucocorticoid treatment for adrenal insufficiency. Participants who remain on corticosteroids to treat adrenal insufficiency must be discussed with the BMS Medical Monitor/designee to continue the study. Rescue therapy with medications other than oral corticosteroids, including immunosuppressants or biologics for IBD, are not permitted.

Oral corticosteroid rescue therapy [REDACTED] may be used [REDACTED] in response to an increase in CD or UC disease activity at the investigator's discretion (refer to [REDACTED]). The oral corticosteroid should be tapered upon demonstrated disease improvement per investigator judgement. The recommended corticosteroid taper is as follows:

- [REDACTED]
- [REDACTED]
- [REDACTED]
- [REDACTED]

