8.2 Discontinuation From the Study

Participants who request to discontinue study treatment ([Section 8.1](#) [Discontinuation From Study Treatment]) will remain in the study and must continue to be followed for protocol-specified follow-up procedures. The only exception to this is when a participant specifically withdraws consent for any further contact with him/her or persons previously authorized by participant to provide this information.

- Participants should notify the investigator of the decision to withdraw consent from future follow-up **in writing**, whenever possible.
- The withdrawal of consent should be explained in detail in the medical records by the investigator, as to whether the withdrawal is from further treatment with study treatment only or also from study procedures and/or post-treatment study follow-up, and entered on the appropriate eCRF page.
- In the event that vital status (whether the participant is alive or dead) is being measured, publicly available information should be used to determine vital status only as appropriately directed in accordance with local law.
- If the participant withdraws consent for disclosure of future information, the Sponsor may retain and continue to use any data collected before such a withdrawal of consent.

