Geboes Score and RHI^{43,49}: The Geboes score and the RHI are instruments used to assess the histological appearance of the mucosa in UC.⁴⁹ The Geboes score evaluates 6 histological features (termed Grades), each of which are scored on ordinal scales. The RHI uses the weighted scores from 4 Grades of the Geboes score to derive a score that ranges from 0 to 33, where higher scores indicate a greater degree of histological disease activity. Both Geboes scores^{50,51} and the RHI⁵² have been used to characterize histological activity in UC.

For determination of the Geboes score and the RHI, biopsies for histological assessment will be obtained as indicated in [Section 2](#) (Schedule of Activities) and evaluated by a central reader. Further details on the biopsy collection and processing for this histological assessment will be provided in the Histopathology Image Review Charter.

The Geboes and RHI assessments will be carried out by the central vendor, who will be responsible for reading and scoring all endoscopies and biopsies.

[REDACTED]

[REDACTED]

[REDACTED]

[REDACTED]

[REDACTED]

9.1.6 **Laboratory Assessments**

The following laboratory tests will be performed according to [Section 2](#) (Schedule of Activities) to gather more information about CD and UC activity: [REDACTED]

[REDACTED]

Stool culture, ova, and parasite evaluation, and *Clostridioides difficile* toxin testing are recommended in order to exclude infectious causes of disease exacerbation, as deemed appropriate by the investigator.

9.2 **Adverse Events**

The definitions of an AE or SAE can be found in [Appendix 3](#).

AEs will be reported by the participant (or, when appropriate, by a caregiver, surrogate, or the participant's legally authorized representative).

The investigator and any designees are responsible for detecting, documenting, and reporting events that meet the definition of an AE or SAE and remain responsible for following up AEs that are serious or considered related to the study treatment or the study, or that caused the participant to discontinue before completing the study.

Contacts for SAE reporting specified in Appendix 3.

9.2.1 **Time Period and Frequency for Collecting AE and SAE Information**

Sections 5.6.1 and 5.6.2 in the IB represent the Reference Safety Information to determine expectedness of SAEs for expedited reporting.

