10.3 Endpoints

10.3.1 Primary Endpoints

The primary objective of this study is to assess the safety and tolerability of long-term use of deucravacitinib in participants with moderate to severe CD or moderate to severe UC. To support this objective, the following endpoints will be assessed:

- Number and proportion of participants experiencing AEs, SAEs, AEs leading to study discontinuation, and AEs.
- Number and proportion of participants experiencing abnormalities in laboratory testing, ECG, and vital sign parameters over time.
- Changes from IM011077 study baseline for laboratory testing, ECG, and vital signs.

[REDACTED]

[REDACTED]

[REDACTED]

[REDACTED]

[REDACTED]

[REDACTED]

[REDACTED]

[REDACTED]

[REDACTED]

[REDACTED]

[REDACTED]

[REDACTED]

[REDACTED]

[REDACTED]

[REDACTED]

[REDACTED]

[REDACTED]

[REDACTED]

[REDACTED]

[REDACTED]

[figure not shown]
[REDACTED]

[figure not shown]
[REDACTED]

[REDACTED]

[REDACTED]

[REDACTED]

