10.4.2.1 Adverse Events

AEs for this study will be collected from the time the participant signs the informed consent form until the Final Safety Visit (ie, 28 days after EOT or ET) at the timepoints specified in [Section 2](#) (Schedule of Activities). AEs that are ongoing from parent studies that worsen after the participant signs the informed consent form will be reported as new AEs in Study IM011077. AEs reported during parent studies that have either resolved or are ongoing [REDACTED] from the parent study end of treatment visit will be recorded as Medical History in Study IM011077.

TEAEs are events that occur after the administration of the first dose of study treatment in Study IM011077. AEs that were ongoing during the parent study and worsen once study treatment is initiated in this study will also be considered treatment emergent. All AEs will be coded using the Medical Dictionary for Regulatory Activities (MedDRA) and presented by System Organ Class and Preferred Term. Serious AEs and deaths, AEs leading to study treatment discontinuation, AEs by maximum severity, and AEs by relationship will also be summarized by the MedDRA System Organ Class and Preferred Term. All TEAEs will also be summarized by Preferred Term sorted by decreasing frequency.

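### Does an endpoint worded as study discontinuation, paired with a planned table of treatment discontinuation, leave a primary safety result undefined?

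*Combined protocol and SAP*

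**What the plan says.** The endpoint appears in five places with the same discontinuation wording. The Synopsis gives it for Crohn's disease and for ulcerative colitis: "Number and proportion of participants experiencing AEs, SAEs, AEs leading to study discontinuation, and AEIs". Tables 4-1 and 4-2 in Section 4 repeat it: "Number and proportion of participants experiencing AEs, SAEs, AEs leading to study discontinuation". Section 10.3.1 lists it among the primary endpoints as "AEs leading to study discontinuation".

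Section 10.4.2.1 sets out the adverse event summaries: all events by System Organ Class and Preferred Term, serious events and deaths, events by maximum severity and by relationship, treatment-emergent events by descending frequency, and "AEs leading to study treatment discontinuation". The last is the only one of these that concerns discontinuation.

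Section 8.1 lists the grounds for stopping study treatment and requires the reason to be documented and entered on the eCRF. Section 8.2 deals with leaving the study. It asks the investigator to record, when consent is withdrawn, "whether the withdrawal is from further treatment with study treatment only or also from study procedures and/or post-treatment study follow-up".

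**The concern.** Sections 8.1 and 8.2 draw a formal line. A participant who asks to stop the drug stays in the study and is followed, and everyone who stops permanently has an early termination visit, a 4-week follow-up and a final safety visit (Sections 5.1.2, 5.1.3 and 8.1.2). On a strict reading, someone who stops the drug because of an adverse event and then attends the final safety visit has discontinued treatment but perhaps not the study. The endpoint would miss that person and the Section 10.4.2.1 table would count them.

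If so, one component of the primary safety endpoint would depend on how the end of participation is coded, and the clinical study report could carry two different numbers under similar names. For a long extension study whose purpose is tolerability, an understated count of adverse event stops would be unwelcome.

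**Working it through.** The protocol states no figure to reproduce. The check is a comparison of the text, followed by one illustration on assumed counts.

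**1. Which route can an adverse event take out of the study?** Section 8.1 includes, among the grounds for stopping treatment, a clinical adverse event, laboratory abnormality or intercurrent illness, with separate entries for significant infection, drug-related rash or hypersensitivity, liver criteria and other laboratory criteria. Section 8.2 describes no exit on account of an adverse event; its subject is requests to stop and withdrawal of consent. Read strictly against 8.2, the endpoint would therefore have almost no defined way of being met, which is unlikely to be the intention.

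**2. How does the protocol use the two terms elsewhere?**

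- Section 8.1 heads its list as discontinuation of treatment, yet words the adverse event ground in terms of continued participation in the study.
- Section 9.2 refers to events "that caused the participant to discontinue before completing the study", whereas Section 9.2.3 speaks of interruption or discontinuation of treatment.
- Section 9.2.5 stops treatment for pregnancy and then calls the next steps study discontinuation procedures.
- Section 7.7.4.1 says of a participant who still meets the criteria despite treatment that "he/she should be identified as a treatment failure, be discontinued from study treatment". Section 7.7.4.2 says that a failed corticosteroid taper "will be considered treatment failure, and participants must discontinue from the study".
- The Amendment 01 rationale for Sections 5.1.2 and 5.1.3 explains text about stopping treatment as a way to make sure that people who discontinue the study attend the safety follow-up visit. This is a rationale and not operative text, but it shows the usage: attending that visit does not stop someone being regarded as having discontinued the study.

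Taken together, these suggest near-synonyms more than two intended counts.

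**3. Are the data for the treatment-stop count collected?** Yes. Section 8.1 puts the reason for stopping on the eCRF. Section 9.2.6 requires a laboratory abnormality that led to discontinuation or interruption to be recorded as an adverse event, so laboratory-driven stops reach the adverse event data too. Sections 9.2.3 and 9.2.6 name interruption separately from discontinuation, which supports reading the Section 10.4.2.1 table as permanent stops, even though Section 8.1.1 uses the word discontinuation for temporary ones.

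**4. How far apart could the readings be?** The documents give no event rate. Assume, for illustration only, that all of about 300 participants (Section 10.1) are dosed, that 10 to 30 stop permanently for an adverse event, and that all of these complete the final safety visit.

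- Treatment reading: 10/300 = 3.3% to 30/300 = 10.0%.
- Strict study reading, if none is coded as leaving the study: 0/300 = 0%.
- If each permanent stop is also coded as leaving the study, the two readings coincide.

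The range runs from no difference to the whole count and depends on coding. The higher figure is tabulated under Section 10.4.2.1 in every case.

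**The case for a change.** The strongest opposing case is that the conflict is literal and sits in a primary endpoint. The phrase occurs five times and the analysis section never uses it. The protocol has separate sections for the two events, and no visible sentence says that they are to be treated as one. A programmer working from the study disposition page could produce a smaller number than one working from the treatment page. Aligning the phrase would cost almost nothing.

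Much of this stands. The terms do differ, and the visible text does not say which count is meant or exactly which grounds in Section 8.1 count as adverse event stops. It cannot be said, however, that the count is undefined: Table 4-3, which holds selected endpoint definitions, is redacted, and Section 10.4.1 (under the efficacy heading) and Section 10.4.3 defer detail to a SAP whose separate text was not supplied.

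What does not stand is the step from loose wording to a result at risk. The table of events leading to treatment discontinuation is planned explicitly, its data are collected, and a reader of the report will see it whatever the endpoint list calls it. Adding a line for study withdrawals is a reporting preference.

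The different wording in Sections 7.7.4.1 and 7.7.4.2 should be reconciled as an instruction for conduct. Both passages concern treatment failure and do not settle how adverse events are counted.

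**Conclusion.** This is a slip of terminology that analysts will resolve sensibly. The component of tolerability that matters, participants who stop the drug because of an adverse event, is already planned for tabulation in Section 10.4.2.1, by parent-study treatment, by indication and overall in the As-treated population (Section 10.4.2). The study is uncontrolled and descriptive, with no sample size calculation, so there is no test or error rate to disturb.

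The difference between the two counts cannot be sized from the documents; the percentages above rest on assumed counts and only mark out the extremes. The conclusion rests on two assumptions: that the Section 10.4.2.1 table is produced as planned, and that the reason for stopping is recorded as Section 8.1 requires. Given those, aligning the phrase would tidy the text but would change no reported result or conclusion that the analysts would not reach anyway. No change to the plan is called for.

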10.4 Statistical Analyses

10.4.1 Efficacy Analyses

Because this study is for observational purposes, no statistical tests for treatment comparisons will be conducted. Categorical data will be summarized as frequency counts and percentages. Continuous data will be summarized using number of participants (n), mean, standard deviation (SD), median, minimum, and maximum unless otherwise specified. Efficacy variables will be summarized for all visits in which the variable is assessed. Complete details of the planned analyses will be documented in the SAP and finalized before database lock. Summaries will be provided for the As-treated population. Participants will be summarized according to the treatment they received in their parent trial.

10.4.1.1 Definition of Baseline

Baseline data are defined as:

- The **parent study baseline** is the baseline efficacy assessment performed in Study IM011023, IM011024, or IM011127 during the enrollment period or the Day 1 visit, as applicable.
- The **IM011077 study baseline** is the last measurement collected on or prior to the date of the first dose in Study IM011077. Relevant laboratory data, along with clinical and PRO assessments from the end of treatment visit in IM011023, IM011024, or IM011127, may constitute the baseline measures for IM011077. These procedures need not be repeated at the baseline visit in IM011077. Any assessments specific to IM011077 will be performed prior to assignment of IM011077 study treatment.

[REDACTED]

[REDACTED]

10.4.2 Safety Analyses

Safety data will be analyzed for AEs, SAEs, laboratory analytes, and vital signs. Safety will be summarized using the As-treated population. Participants will be summarized according to the treatment they received in their parent trial, as well as by indication and overall. Categorical data will be summarized as frequency counts and percentages. Continuous data will be summarized using n, mean, SD, median, minimum, and maximum unless otherwise specified.

10.4.2.1 Adverse Events

AEs for this study will be collected from the time the participant signs the informed consent form until the Final Safety Visit (ie, 28 days after EOT or ET) at the timepoints specified in [Section 2](#) (Schedule of Activities). AEs that are ongoing from parent studies that worsen after the participant signs the informed consent form will be reported as new AEs in Study IM011077. AEs reported during parent studies that have either resolved or are ongoing [REDACTED] from the parent study end of treatment visit will be recorded as Medical History in Study IM011077.

TEAEs are events that occur after the administration of the first dose of study treatment in Study IM011077. AEs that were ongoing during the parent study and worsen once study treatment is initiated in this study will also be considered treatment emergent. All AEs will be coded using the Medical Dictionary for Regulatory Activities (MedDRA) and presented by System Organ Class and Preferred Term. Serious AEs and deaths, AEs leading to study treatment discontinuation, AEs by maximum severity, and AEs by relationship will also be summarized by the MedDRA System Organ Class and Preferred Term. All TEAEs will also be summarized by Preferred Term sorted by decreasing frequency.

